#### 2.2. Secondary Objectives

- To examine differences in vaccination rates between individuals in CVD-I who engaged with different numbers of intervention messages, and changes in self-reported vaccination rates following intervention messages
- To describe levels of engagement with the intervention messages and perceptions of the intervention messages within the CVD-I group
- To examine predictors of vaccination status, including cardiovascular condition type, vaccine drivers/barriers, and vaccine knowledge, across diagnoses and within CVD-I and CVD-C groups

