#### 8.2.3. Analysis of Secondary Endpoint

To examine differences in vaccination rates between individuals in the CVD-I group and its relationship to engagement with intervention messages, we will model:

$$logit(Y) = \beta_0 + \beta_1 M + \sum_i \beta_i \alpha_i + \varepsilon$$

Where:

logit(Y) = ln(Y/1-Y) for the binary variable designation of influenza status

M = the number of engaged messages (ordinal variable 0, 1, 2, 3, 4, 5, 6)

 $\alpha_j$  = the baseline covariates measured in the study (e.g. demographics, vaccine drivers/barriers, or knowledge)

To examine predictors of vaccination status, including cardiovascular condition type, vaccine drivers/barriers, and vaccine knowledge, across CVD-I and CVD-C we will construct the model:

$$logit(Y) = \beta_0 + \beta_1 P + \sum_i \beta_i \alpha_i + \varepsilon$$

Where:

logit(Y) = ln(Y/1-Y) for the binary variable designation of influenza status

 $C_i$  = the binary designation Cardiovascular Condition as described earlier

P = the predictor of interest (e.g. cardiovascular condition, vaccine drivers/barriers, vaccine knowledge index)

 $\alpha_j$  = the baseline covariates measured in the study (e.g. demographics, vaccine drivers/barriers, or knowledge)

 $\varepsilon$  = the error term of the regression.

To examine predictors of vaccination status, including cardiovascular condition type, vaccine drivers/barriers, and vaccine knowledge, within CVD-I or CVD-C we will construct the model:

$$logit(Y) = \beta_0 + \beta_1 M + \beta_2 P + \sum_i \beta_i \alpha_i + \varepsilon$$

Where:

logit(Y) = ln(Y/1-Y) for the binary variable designation of influenza status

M = the messaging group being examined (either Intervention or Control)

P = the predictor of interest (e.g. cardiovascular condition, vaccine drivers/barriers, vaccine knowledge index)

 $\alpha_j$  = the baseline covariates measured in the study (e.g. demographics, vaccine drivers/barriers, or knowledge)

 $\varepsilon$  = the error term of the regression.

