3.2 Secondary objectives

The secondary endpoints in this study will examine:

- Predictors of vaccination status, including cardiovascular condition type, vaccine drivers/barriers, and vaccine knowledge, across and between CVD-I and CVD-C.
- Engagement with interventions, including clicking, opening, or completing the intervention messages

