7.1 Derived Data

Cardiovascular condition type will be one of the following for the purposes of the secondary analysis objectives:

- People with self-reported arrhythmia only (not including atrial fibrillation)
- People with self-reported atrial fibrillation only
- People with self-reported heart attack, cardiac arrest or coronary artery disease only
- People with self-reported congestive heart failure only
- People with self reported stroke only
- People with two or more of the above conditions
- People with other cardiovascular conditions

Vaccine drivers and barriers of interest include:

- Number of visits to a primary care provider in the 3 months prior (categorized as None, 1-2, 3 or more)
- Number of visits to a cardiology specialist in the 3 months prior (categorized as None, 1-2, 3 or more)
- Hospitalization in the 3 months prior (categorized as none, once, 2 or more)
- Offered influenza vaccination by a healthcare provider (categorized as Yes, No, Unsure)
- Healthcare provider informed individual they were in a 'high risk group' (categorized as Yes, No, Unsure)

Vaccine knowledge factors are based on responses to the survey question "What sources of information do you use to learn about the flu vaccine?", with possible responses:

- Healthcare Professionals
- Family member or peers
- Social media including blog posts
- Mobile applications
- Conventional news media (e.g. television, newspapers)

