8.5 Primary objective analysis

An intention to treat analysis will be conducted of the primary outcomes for the study. Assuming that a descriptive comparison of the intervention to the control group does not demonstrate statistically significant differences in terms of demographics, vaccine drivers/barriers, or vaccine knowledge, we will report on the relative rate of influenza vaccination for the intervention group compared to the control group. This is given simply by:

RR = rate of influenza vaccination among intervention group rate of influenza vaccination among control group

We will also conduct logistic regression modeling of influenza vaccination as follows:

$$logit(Y) = \beta_0 + \beta_1 M + \sum_i \beta_i \alpha_i + \varepsilon$$

Where:

logit(Y) = ln(Y/1-Y) for the binary variable designation of influenza vaccination status M = the binary designation for Intervention (messaging) vs Control (no messaging) $\alpha_j = the$ baseline covariates measured in the study (e.g. demographics, vaccine drivers/barriers or knowledge) $\epsilon = the$ error term of the regression.

Vaccine drivers and barriers are described above in Section 8.1: Derived Variables

For the logistic regression model the p-values, odds ratio and associated 95% CI associated with each of the β parameter estimates will be reported.

Kaplan-Meier curves will be constructed for time-to-influenza vaccination, using the participant estimated dates of influenza vaccination from the 3 and 6 month surveys.

- 8.6 Secondary objective analysis
- 8.6.1 To examine predictors of vaccination status, including cardiovascular condition type, vaccine drivers/barriers, and vaccine knowledge, across and between CVD-I and CVD-C.

To examine predictors of vaccination status, including cardiovascular condition type, vaccine drivers/barriers, and vaccine knowledge, across CVD-I and CVD-C we will construct the model:

$$logit(Y) = \beta_0 + \sum_i \beta_i P_i + \sum_i \beta_i \alpha_i + \varepsilon$$

Where:

logit(Y) = ln(Y/1-Y) for the binary variable designation of influenza vaccination status P_i = the predictor of interest i (e.g. cardiovascular condition, vaccine drivers/barriers, vaccine knowledge) α_j = the baseline demographics ϵ = the error term of the regression.

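### SAP 8.6.1 estimates cardiovascular condition type only alongside healthcare-contact drivers, so no planned result shows whether vaccination differs between condition types

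*Protocol*

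**What the plan says.** The objective appears in Protocol 2.2 as "To examine predictors of vaccination status, including cardiovascular condition type, vaccine drivers/barriers, and vaccine knowledge, across diagnoses and within CVD-I and CVD-C groups" and in SAP 3.2 as "Predictors of vaccination status, including cardiovascular condition type, vaccine drivers/barriers, and vaccine knowledge, across and between CVD-I and CVD-C". Condition type is thus a predictor in its own right, beside drivers/barriers and knowledge.

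Protocol 8.2.3 fits one predictor at a time, "the predictor of interest (e.g. cardiovascular condition, vaccine drivers/barriers, vaccine knowledge index"). The covariates around it are described as "the baseline covariates measured in the study (e.g. demographics, vaccine drivers/barriers, or knowledge"), which is a list of examples joined by an 'or'.

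SAP 8.6.1 replaces the single predictor by a sum over predictors, each being "the predictor of interest i (e.g. cardiovascular condition, vaccine drivers/barriers, vaccine knowledge"), with baseline demographics as the remaining covariates. Its second model, for differences between the arms, sums predictor-by-arm terms over the same set. Both report adjusted odds ratios with p-values and 95% CI, and SHAP values.

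SAP 7.1 fixes what the drivers are (SAP 8.6.1 cites this as section 8.1). They include "Number of visits to a cardiology specialist in the 3 months prior (categorized as None, 1-2, 3 or more") and "Hospitalization in the 3 months prior (categorized as none, once, 2 or more"), and also primary care visits, whether a provider offered the vaccine, and whether a provider told the person they were at high risk. Knowledge is represented by the sources of information used.

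**The concern.** Visits, warnings and offers may come about partly because of the diagnosis. If so, holding them fixed takes out of the condition-type odds ratio whatever part of the difference runs through them. The joint model asks whether people with the same visits, warnings and offers differ by diagnosis. The objective can equally be read as asking whether diagnosis groups differ in vaccination, and nothing in the plan answers that.

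The SHAP values do not fill the gap, because they come from the same fitted model. In their usual form for a linear predictor they are the coefficient times the deviation from the mean, so they shrink with the coefficient.

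What is at stake is one named secondary objective. A group that is less vaccinated because it is seen, warned and offered less could show an odds ratio near 1, with no other planned result to reveal the difference. The primary comparison is not affected.

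**Working it through.** **What is planned by condition type.** SAP 8.6.1 gives driver-adjusted estimates only. SAP 8.4 and Protocol 8.2.1 describe vaccination rates among participants and compare the arms, not the diagnoses. The chi-square sentence in SAP 8.1 is general and is not assigned to this question. Protocol 8.2.4 aggregates complications and wearable data by condition, not vaccination. So no crude or demographics-only comparison is planned.

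**Inputs.** The documents give no figure for this analysis and no driver rates or effects. Their sample-size figures concern the arms (the 50% vs 53% row, 8,710, reproduces as 8,711). Everything below is assumed, except the analysed total of about 8,000, which sets the scale of the group sizes.

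**Exact calculation under full mediation.** Assume told high risk in 25% without a cardiology visit and 60% with one; vaccine offered in 35% and 70%; told and offered independent given the visit. Vaccination follows logit P = −0.8 + ln(1.2)·visit + ln(1.6)·told + ln(3)·offered, with no diagnosis term.

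Summing over neither, told only, offered only, both:

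- No visit: 0.4875×0.3100 + 0.1625×0.4182 + 0.2625×0.5741 + 0.0875×0.6832 = 0.4296
- Visit: 0.12×0.3503 + 0.18×0.4631 + 0.28×0.6180 + 0.42×0.7213 = 0.6014

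A group's rate is therefore 0.4296 + 0.1718 × P(visit), and the difference between two groups is 17.18 points times their difference in P(visit).

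| Visit, group A vs B | Vaccinated | Difference (points) | Odds ratio without drivers |
|---|---|---|---|
| 40% vs 45% | 49.8% vs 50.7% | 0.9 | 1.03 |
| 40% vs 50% | 49.8% vs 51.5% | 1.7 | 1.07 |
| 40% vs 70% | 49.8% vs 55.0% | 5.2 | 1.23 |
| 30% vs 80% | 48.1% vs 56.7% | 8.6 | 1.41 |

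With weaker odds ratios (told 1.3, offered 2), 40% vs 50% gives 1.2 points and 40% vs 60% gives 2.5 (43.2% vs 45.7%). With stronger ones (told 2, offered 4), 30% vs 80% gives 10.1 (52.6% vs 62.7%). In every case the driver-adjusted odds ratio for diagnosis is 1.00, because the model was built without a direct effect. That 1.00 is an assumption, not a result.

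**Simulation, allowing a direct effect.** Two diagnosis groups of 800 vs 2,400 (or 400 vs 2,400), 600 replicates per scenario. Cardiology visit, hospitalisation, told and offered occur in 35%, 8%, 35% and 50% of the larger group, and in 25, 8, 25 and 15 points more of the smaller group, or half those increments. Log-odds for vaccination are 0.2, 0, 0.5 and 1.0; the intercept is −0.75. Tests are two-sided at 5%.

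| Direct log-odds of diagnosis | True difference (points) | Odds ratio without / with drivers | Detected without drivers | Detected with drivers |
|---|---|---|---|---|
| 0, half increments | 3.8 | 1.17 / 1.00 | 28–46% | 4–5% |
| 0, full increments | 7.6–7.8 | 1.36–1.37 / 0.99–1.01 | 81–96% | about 5% |
| 0.1 to 0.2 | 6–12 | 1.29–1.66 / 1.10–1.23 | 63–100% | 11–62% |

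With no direct effect, the model with drivers rejects at about the false-positive rate. With a direct effect, the association is weakened but not erased.

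**The case against.** The strongest reply is that examining predictors does not promise a total effect of diagnosis. A mutually adjusted model is a legitimate way to ask which factors predict given the others, and the SAP labels its odds ratios as adjusted. This stands: the joint model validly answers whether condition type adds anything beyond healthcare contact and advice. The plan is incomplete on this objective rather than invalid, and a reader who infers that the objective would be answered wrongly goes further than the documents allow.

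A reader might also infer from Protocol 8.2.3 that condition type must be adjusted for drivers. Its wording, with examples and an 'or', does not commit to that; a demographics-only version would fit it. The point rests on SAP 7.1 and 8.6.1.

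It is fair, too, that the drivers need not all follow from the diagnosis. Visits to primary care and hospitalisation are not restricted to cardiac causes, so they may partly reflect comorbidity, where adjustment is defensible. No passage gives a causal order among the drivers, so a stepwise scheme that enters visits first and offers later has no basis in the documents.

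Measuring the drivers at baseline would not settle the matter, since they could still lie between diagnosis and vaccination. The survey schedule collects them at baseline, month 3 and month 6, and the SAP does not say which survey supplies the values for 8.6.1.

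**Conclusion.** The point holds as a gap in the planned results. SAP 8.6.1 delivers a driver-adjusted association for condition type, and nothing planned shows vaccination by condition type without the drivers. A real difference can be attenuated, or hidden if diagnosis acts wholly through the drivers.

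The size is hypothetical. Under the full-mediation inputs above it runs from about 1 to 10 points, and it tends to zero as the diagnosis groups become more alike in healthcare contact. A reader might infer that condition type will come out null; the documents do not support that, because they say nothing about how far diagnosis works through the drivers, and under partial mediation the joint model still detected it in 11–62% of replicates. The 3-point effect assumed for the arms is not a benchmark here, since it belongs to a different comparison. This is a low-cost improvement to a secondary objective.

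**What to change.** In SAP 8.6.1:

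1. Add one logistic model in population P1 of vaccination on condition type with baseline demographics and arm only. Report an overall test across the types (up to 6 degrees of freedom for the seven categories in SAP 7.1) and adjusted vaccination rates with 95% CI per type. Name this as the condition-type result. Rates are useful here because odds ratios from models with different covariates are not directly comparable.
2. Add the matching condition-type-by-arm model without drivers, for the between-arm part of the objective.
3. Keep the present joint models, and label their condition-type estimates and SHAP values as driver-adjusted associations, that is, what is left after healthcare contact, provider advice and information sources.
4. State which survey supplies the driver values.

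No new data or participants are needed. The cost is a short SAP edit, two further model fits, and a longer results table that shows two odds ratios for condition type and must explain the difference between them.

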#### 8.2.4. Exploratory Analyses

To examine the potential impact of COVID-19 on vaccination rates, we will add a term to the model used in the primary analysis model:

Version 1 18 of 22

$$logit(Y) = \beta_0 + \beta_1 M + \sum_j \beta_j \alpha_j + \beta_c c + \beta_i M * c + \varepsilon$$

Where the additional term c is the Covid-19 status (1 if diagnosed with COVID-19, 0 if not) and the parameter estimate for the interaction term,  $\beta_i$  will be reported. Similarly, we can also evaluate the effect of COVID-19 attitudes towards influenza vaccination rates. In this case, the term c would represent COVID-19 attitudes (1 if the participant reports more likely to vaccinate, 0 if the person does not).

To describe self-reported complications from influenza experienced by individuals with different cardiovascular conditions during the 6-month study period, as well as differences in complications by vaccination status, we will aggregate rates of self-reported complications by cardiovascular conditions, as well as by vaccination status.

To examine differences in wearable data (i.e., sleep, steps, heart rate) between individuals who experience influenza and those who do not, as well as differences in wearable data between cardiovascular conditions, we will aggregate day-level wearable data over the entire study period based on influenza status, as well as by cardiovascular condition.

Between-group comparisons of the outcomes described above (e.g. self reported complications or mean daily steps) will be conducted with Student's t-tests or the non-parametric Mann-Whitney U test when appropriate, with correction for multiple testing using the Benjamini-Hochberg approach for False Discovery Rate correction.

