8 STATISTICAL METHODS

8.1 General Statistical Approaches

For the study variables, we will perform distributional analysis. When describing the study population, we will use min, max, mean, and standard deviations for continuous variables (i.e. age, BMI) and frequency counts for categorical variables (i.e. gender, ethnicity). For both continuous and categorical variables, we will report on the number of participants evaluated for that variable, as well as the number of people with non-missing values. For the study variables, we will also look at individual-level rates of missing data. Missing data or unknown responses will be described separately and not be counted in the summary descriptions of the variables. We will report on the percent of missing data for each of the included data sources (surveys, activity data) and evaluate whether any missingness is associated with baseline participant-level characteristics in the case of missing survey data or with the outcome in the case of activity tracker data.

Statistical testing comparing variables will be performed at the 5% significance level using two-sided tests or two-sided 95% confidence intervals (CI), unless otherwise specified. Comparison of means will use Student's t-test for normal distributions, or a Mann-Whitney U test for non-normal distributions. Comparisons of frequencies will use chi-square tests. Regression modeling approaches are described below. We will report on the size of the beta-parameter estimate and the associated significance level (p-value) for each predictor variable.

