8.7.2 To examine differences in wearable data (i.e., sleep, steps, heart rate) between individuals who experience influenza and those who do not, as well as differences in wearable data between cardiovascular conditions.

Participants are asked if they were diagnosed with influenza infection in the preceding 3 months for the 3-month and 6-month survey. Differences in daily steps per day, total sleep hours and resting heart rate will be aggregated over the 3 month period and compared among people who report having influenza to those who do not. Similar comparisons within each type of cardiovascular condition will also be performed.

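### The SAP leaves out the protocol's Benjamini-Hochberg correction for the exploratory wearable comparisons and does not declare the change

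*Protocol*

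**What the plan says.** Protocol 8.2.4 covers the exploratory outcomes, wearable measures included: "Between-group comparisons of the outcomes described above (e.g. self reported complications or mean daily steps) will be conducted with Student's t-tests", or with Mann-Whitney U tests where appropriate, "with correction for multiple testing using the Benjamini-Hochberg approach for False Discovery Rate correction". It gives no FDR level and does not define the family of tests.

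SAP 8.1 sets a general rule: "Statistical testing comparing variables will be performed at the 5% significance level using two-sided tests or two-sided 95% confidence intervals (CI), unless otherwise specified". It keeps the protocol's two tests: "Comparison of means will use Student's t-test for normal distributions, or a Mann-Whitney U test for non-normal distributions". No multiplicity correction appears there.

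SAP 8.7.2 describes the wearable analysis: "Differences in daily steps per day, total sleep hours and resting heart rate will be aggregated over the 3 month period and compared among people" with and without reported influenza. It then adds: "Similar comparisons within each type of cardiovascular condition will also be performed". Its heading also names differences between cardiovascular conditions. It sets no other significance level and no correction.

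SAP section 6, which lists changes to the protocol's statistical section, contains one item: the objective on influenza complications is removed.

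**The concern.** The protocol promises adjusted results for these comparisons, and the SAP as written would produce unadjusted ones. The same data could then support different claims depending on which document the analyst follows. The SAP also enlarges the set of tests. The protocol aggregates wearable data over the whole study period, whereas the SAP uses a 3-month period, asks about influenza at both the 3-month and 6-month surveys, and repeats the influenza comparison inside each condition type. The number of comparisons grows while the safeguard written for them is no longer mentioned. At stake is which wearable differences are called significant.

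**Working it through.** The documents give no error rate, FDR level or number of tests for this analysis, so there is no figure of the plan's own to reproduce.

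**Inputs**
- Level per test: 0.05, two-sided (SAP 8.1).
- Measures: 3, namely daily steps, total sleep hours and resting heart rate (SAP 8.7.2).
- Groups: overall plus 7 condition types. The seven come from SAP 7.1, which introduces the list thus: "Cardiovascular condition type will be one of the following for the purposes of the secondary analysis objectives". Applying it to an exploratory analysis is an assumption.
- Windows w: 1 or 2. SAP 8.7.2 does not say whether the two survey periods are pooled.

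**Number of tests**

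m = 3 × (1 + 7) × w = 24 for one window, 48 for two. Comparisons between condition types are not counted, because the SAP does not say how they would be made.

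**Unadjusted testing with no true differences**

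Expected false positives = 0.05 × m, whatever the dependence. Chance of at least one, if tests are independent = 1 − 0.95^m.

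| Set of tests | m | Expected false positives | Chance of at least one |
|---|---|---|---|
| Overall only, one window | 3 | 0.15 | 14.3% |
| Overall only, two windows | 6 | 0.30 | 26.5% |
| Overall + 7 types, one window | 24 | 1.2 | 70.8% |
| Overall + 7 types, two windows | 48 | 2.4 | 91.5% |

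**Dependence**

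The tests are not independent. The three measures come from the same people, the two windows may be correlated, and the overall test is built from the condition types. The condition types themselves are disjoint groups of people, so a single common correlation across all tests would be the wrong model. A simulation with this structure used 200,000 replicates per setting, seven equally weighted types, correlation between measures of 0, 0.3 or 0.6, and correlation between windows of 0 or 0.5. The chance of at least one false positive was:
- 24 tests: 61-68%
- 48 tests: 82-90%
- three overall tests, one window: 12-14%

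**Sensitivity to the seven types**
- Six types: 3 × 7 = 21 or 42 tests, giving 66% or 88% under independence.
- The five single-condition types only: 3 × 6 = 18 or 36 tests, giving 60% or 84%.

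**With the correction**

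With Benjamini-Hochberg at 5% (assumed, since the protocol states no level), the chance of any false positive in the same simulations was 4.3-5.0%. This is as expected: when every null is true, any rejection is false, so the false discovery rate equals the chance of any rejection. When some effects are real, the method controls the expected proportion of false findings, not the chance of any.

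**The case against.** The strongest reply is that the SAP is silent and does not reject the correction. Its 5% rule is a default with an exception clause, a 5% level is compatible with adjusted p-values, and because section 6 does not withdraw the correction, the protocol's commitment could be read as still in force. This stands in part: a reader might infer that the sponsor decided to abandon the correction, and the documents do not show that. But SAP 8.7.2 specifies nothing other than the default, so an analyst working from the SAP would test without adjustment.

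A reader might also infer that false positive wearable findings are likely whatever is analysed. The documents do not support that. The high figures need the full set of 24 to 48 tests and no true difference in any of them. The background sections of both documents cite earlier work in diabetes in which people with influenza were less active and had a raised heart rate, so some of these differences may be real, leaving fewer null tests.

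The count of seven types is also soft. The list was written for another objective, and the category for other conditions may be nearly empty, since eligibility requires one of the named conditions. Dropping it changes the figures only modestly, as shown above.

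Finally, the scope is narrow. The complications objective has been removed (SAP 8.2 still assigns it a population, but SAP 8.7 plans no analysis of it) and the COVID-19 objective is descriptive, so only the wearable comparisons are affected. That limits the weight of the point. It does not remove it, because the protocol itself chose to correct these exploratory comparisons.

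**Conclusion.** The point holds as an undeclared omission that leaves the two documents in conflict. Under the SAP default, each wearable comparison would be tested at an unadjusted 5%. For the influenza yes/no comparisons, and if no true differences exist, that means 1.2 expected false positives in 24 tests or 2.4 in 48. The chance of at least one is 71% or 91% under independence, and about 61-68% or 82-90% with plausible dependence. These figures rest on the seven-type list applying, on the number of windows tested, and on the global null. They leave out any between-condition comparisons. The primary and secondary conclusions do not depend on this. It should be corrected because it changes which wearable results are called significant and the remedy is already in the protocol.

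**What to change.** Add to SAP 8.7.2:

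> P-values for all wearable comparisons (three measures; by influenza status overall and within condition types, and between condition types; all survey windows tested) form one family and are adjusted by the Benjamini-Hochberg method specified in protocol 8.2.4, at an FDR level of 5% (level set here, as the protocol states none).

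The sponsor should confirm the 5% level and the family, since the protocol fixes neither. If the correction was dropped on purpose, the alternative is to list and justify its removal in SAP section 6.

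The cost is one sentence and slightly fewer nominally significant exploratory results.
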